1.6	5 JULY 2019	Changes to the recruitment process have been recorded in line with DSMB recommendations. Clinicians will no longer be the point of referral. All referrals will be submitted by designated agency staff in line with PHI regulations. Method of referral per agency site has been described therein. Changes to the first call scripts have been edited and updated. DSM-H research study information cards with research team contacts have been included in the recruitment process. Minor formatting edits included.
1.7	31.JAN 2020	Added recruitment method for sites: CNS and FIRSTAT. The updated process will include a designated agency point of contact who will generate a daily potential patient referral report in line with PHI regulations of newly admitted persons with dementia aged 65+ who live in a private residence. The report will be made accessible designated research team for the purpose of referral submissions. In addition, edits to better clarify reporting process of adverse events has also been included. Updated [name] contact information.
1.8	3.JUNE 2020	The protocol has been modified to change the modality of subject visits to virtual from in-person. To achieve this, Inclusion criteria additions: internet capabilities; caregiver 8+hrs of care management per week; edit retention strategies to replace "magnet" with email visit schedule; change the need for subjects to be together for virtual visits 2-4; add QDRS score

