### 5 Study Enrollment and Withdrawal for PWD-Caregiver Dyads

#### 5.1 Inclusion Criteria

1. PWD over the age of 65
2. Admitted to one of the three HHC agencies
3. The patient and family caregiver speak English and/or Spanish.
4. The informal caregiver is ≥18 years of age and manages the PWD's care for at least 8 hours per week.
5. Patients who score ≥6 on the Quick Dementia Rating Scale (at least mild impairment).
6. PWD and the caregiver have internet connection.

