## **7 Study Procedures and Schedule**

### **7.1 Study Procedures/Evaluations**

#### **7.1.1 Study Specific Procedures**

All data will be collected virtually via telephone and through internet capabilities. The following questionnaires will be collected by the research team as part of research assessment of efficacy of the intervention as it relates to the aims for both performance improvement and control subjects:

- Quick Dementia Rating Scale (QDRS): Is a 10-item tool that measures cognitive impairment based on the severity of dementia.
- Neuropsychiatric Inventory Questionnaire (NPI-Q): Is a 13-item tool that measures caregiver perceptions of dementia BPSD presence and severity.
- Quality of Life in Alzheimer's Disease (QOL-AD): Is a 13-item tool that measures caregiver perceptions of quality of life in the PWD
- PAINAD: Is a pain assessment tool for use in persons with moderate to severe dementia who cannot provide reliable report.
- Brief Pain Inventory Short Form (BPI) is a 9-item tool that measures pain location, severity and intensity.
- FAM-CAM: Is an 11-item tool that is an informant-based assessment of delirium.
- Medication Record and use: We will create a list of medications the PWD is taking as well as the frequency of administration of any PRN medications taken, including any OTC or herbal supplements. The primary reason for collecting this data is to examine analgesic and antipsychotic use.
- Caregiver Targeted Quality of Life Tool (CGQOL): Is an 80-item tool with 10 domains for measuring the quality of life of the caregiver of the PWD.
- Public Health Questionnaire 9 (PHQ-9): Is a 9-item tool that measures depressive symptoms.
- Zarit Burden Inventory: Is a 22-item tool that measures caregiver burden.
- SF-12: The SF-12 is a 12-item tool that measures functional health and well-being.
- ADLs and IADLS: Are 12 items that measure functional status as part of the QOL-AD.
- Charlson Comorbidity Index: Is a reliable and valid comorbidity assessment tool.
- The Short Assessment of Health Literacy (SAHL): Is an 18-item test designed to examine health literacy levels
- Other non-instrumented questions that will be asked include sociodemographics (DOB, sex, highest education level attained, race, ethnicity, primary language, religion, marital status, household members, number type and frequency of unpaid and paid caregivers, and primary care provider name and contact for both PWD and caregiver.

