**CONFIDENTIAL**

This material is the property of the NYU School of Medicine and Langone Medical Center. Do not disclose or use except as authorized in writing by the study sponsor

- Information obtained from the chart includes: Number of visits by the home healthcare staff by type, comorbidities.
- Resource Utilization Inventory: Is a 13-item tool to measure healthcare resource utilization.
- HHCAHPS: Is a 32-item standardized patient satisfaction survey. While home healthcare agencies attempt to collect this on all patients, they are not always successfully able to do so and we will therefore measure independently to avoid missing data.
- Investigator derived questions asking if their caregiving practices have shifted due to the COVID-19 pandemic. The COVID-19 related questions are included in the subject dyad instruments.

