## 10.4 Description of Statistical Methods

### 10.4.1 General Approach

Data Analysis will be performed using SAS 9.4. We will perform statistical tests to examine baseline differences between the quality improvement program and control groups. We will then perform unadjusted comparison of both primary outcomes (patient and caregiver quality of life, emergency room visits) and secondary outcomes (pain, BPSD, delirium, caregiver depression burden, and burnout, hospital and emergency room admissions) between groups. We will focus on the endpoint measure for quality of life, and 30 and 60-day outcomes for emergency room utilization. For primary and secondary outcomes, we will perform a time trend analysis using a mixed effects linear model (PROC MCM). Mixed effects regression is used to analyze longitudinal data with repeated measures accounting for intra-individual and group clustering. We intend to use multivariate mixed effects regression modeling as opposed to traditional linear modeling or ANOVA in order to control for unobservable confounding variables that are constant over time but differ across PWD and/or caregivers. For both primary and secondary outcomes, we will then repeat the above analyses adjusting for baseline variables as covariates for a more efficient measurement of the effects of the quality improvement program. We will also perform correlation analyses to explore the relationship between pain and BPSD, and PWD and caregiver QOL through plotting scores over time and then if a significant correlation is present through adding to our mixed effect model. For utilization data, we will perform logistic regression to examine whether the patient is more or less likely to have a hospitalization or ER visit compared when receiving the quality improvement program at 30 and 60 days. We will then perform a Poisson Count Regression to compare the total number of hospitalizations and ER visits at each timepoint. In these models we will utilize a random effect to measure for clustering.

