## 10.5 Sample Size

Power analyses were conducted using Optimal Design software. Given that this study is randomized at the cluster level, we must control for intra-class correlation, and have therefore calculated all power with an intra-class coefficient of .05, which is more conservative than the most recent clustered palliative care study and aligns well with prior community-based cluster trials. The Quality of Life in Alzheimer's Disease as the primary outcome measure in aim 1 has an average score of 33.1, standard deviation of 5.9. A .5 standard deviation difference in this measure would be clinically meaningful. Therefore, in a 2-sample comparison with a power of .80, an alpha of .05 and covariates that account for a cumulative 15% of the variance in outcome would require 15 dyads per cluster, and 20 clusters (10 per arm) at 60 days to detect a medium effect ( $\delta = .45$ ). For mixed effects linear models, the projected sample size will also allow us to detect a medium linear treatment effect ( $\delta = .45$ ) between groups in unadjusted analyses (assuming 15 dyads per cluster, 20 clusters, 4 observations, and an ICC = .05). Although there are no closed-form equations for calculating the power of linear models that include covariates, any non-zero correlation between covariates and the outcome will reduce the unexplained (error) variance thus increasing the statistical power of our tests, and reducing the minimum detectable effect size. As such, the detectable effect size estimated for the unadjusted analyses can be considered an upper bound estimate for the effect size detectable in adjusted analyses. **We will recruit until we have reached 15 completed cases in each cluster (N=300).** Conservatively anticipating a 15% dropout over the 60 days requires a **total recruitment goal of 345 dyads**. As almost 20,000 patients are seen each year in the three HHC agencies in this study, approximately 30% with ADRD, we do not expect any difficulty recruiting this sample, even with an unanticipatedly high rate of dyads declining to participate.

In addition, for fidelity monitoring, as discussed in section [6.1.6.1](#), we will consent **300 clinicians** at the participating HHC agencies on usual care and quality improvement care teams to complete fidelity monitor by performing the DSKA survey. These clinicians are not study subjects but will be consented as they are

CONFIDENTIAL

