#### 13.3.2 Consent Procedures and Documentation

Informed consent is a process that is initiated prior to the individual's agreeing to participate in the study and continues throughout the individual's study participation. Extensive discussion of risks and possible benefits of participation will be provided to the participants and their families. Consent forms will be IRB-approved and the participant will be asked to read and review the document. The investigator will explain the research study to the participant and answer any questions that may arise. All participants will receive a verbal explanation in terms suited to their comprehension of the purposes, procedures, and potential risks of the study and of their rights as research participants. Following the COVID-19 pandemic the method of completing informed consent with participants has transitioned from an in-person written consent to remote with electronic signature. Where verbal consent is needed, the researcher will incorporate HIPAA authorization language to describe the study purpose, the type of questions asked and their ability to refrain from answering, the length of time expected of their participation, the method for keeping information confidential and who they may contact (PI; IRB) with questions, and that their participation is voluntary and can be stopped at any time without consequence to the PLWD's treatment. The participants are given an opportunity to discuss the study with their surrogates or think about it prior to agreeing to participate. Participants will have the opportunity to carefully review the electronic consent form and ask questions prior to signing and/or providing verbal consent. The participant will electronically sign the informed consent document prior to any procedures being done specifically for the study. Only in cases where the subject due to lack of internet or poor computer literacy cannot electronically sign the consent form, we will accept their verbal consent to participate after all information on the consent document has been presented to them ensuring that regulatory HIPAA language has been heard and all questions have been answered. In these situations where verbal consent is received, the research will date and sign the informed consent document and advise the participant of their enrollment status, confirm with the subject that they want to participate, and then ask the subject if the researcher may begin the visit one assessments. In the cases where verbal consent, as a secondary option has been provided by the participant, a copy of the consent form completed with the researcher's signature will be sent to them and we will reconfirm their participation at visit 2. Where one part of the caregiver-PWD dyad can sign electronically and the other cannot, we will capture the signature of the individual who can sign, and verbal consent of the individual who cannot following said process, as they may be in different locations with differential access to internet. The participants may withdraw consent at any time throughout the course of the trial. A copy of the electronically signed informed consent document will be downloaded by participants for their records. The rights and welfare of the participants will be protected by emphasizing to them that the quality of their medical care will not be adversely affected if they decline to participate in this study.

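### Visits went from in-person to virtual during enrolment and each team recruits to its own quota, but no model in section 10.4.1 carries enrolment period

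*Combined protocol and SAP*

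**What the plan says.** The revision history for version 1.8 (3 June 2020) records: "The protocol has been modified to change the modality of subject visits to virtual from in-person". The current text agrees. Section 7.1.1 says "All data will be collected virtually via telephone and through internet capabilities", and 13.3.2 says that "the method of completing informed consent with participants has transitioned from an in-person written consent to remote with electronic signature". The same version brought in the criterion "PWD and the caregiver have internet connection" (5.1), replaced the 3D-CAM with the FAM-CAM and added COVID-19 items, described in 7.1.1 as "Investigator derived questions asking if their caregiving practices have shifted due to the COVID-19 pandemic".

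Section 5.4 plans enrolment from month 6 of year 1 to month 9 of year 4, which it counts as 3 years and 3 months. Section 10.6.1 randomises care teams once, at the start, in strata of agency and geographic location. Section 10.5 sets the stopping rule by team: "We will recruit until we have reached 15 completed cases in each cluster". Section 5.6 instead stops the whole trial at about 345 enrolled dyads.

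For the analysis, 10.4.1 gives unadjusted comparisons, mixed models, and logistic and Poisson models for utilisation. It then says "we will then repeat the above analyses adjusting for baseline variables as covariates for a more efficient measurement". The only list of baseline variables in section 10 is in 10.4.4: age, sex, education, race, ethnicity, health literacy, functional status and comorbidities. Section 10.4.6 takes subgroups by age, sex and race/ethnicity. Enrolment period, visit mode and the COVID-19 items appear in none of these, and 10.1 says there will be no formal SAP.

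**The concern.** Dyads on either side of the switch differ in how they were interviewed, in one eligibility criterion and in the circumstances of care. Any of these can be related to the outcomes, above all to ER visits and admissions.

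Randomising teams once does not balance calendar time between the arms. A team that fills quickly supplies mostly early dyads, and a slow team supplies later ones. With 10 teams per arm the shares can drift apart, and nothing in the allocation or the models corrects this. The random team effect absorbs part of the resulting variation between teams, but it does not remove an imbalance between arms. The Aim 3 target is a 10% reduction (4.2.1), so even a modest imbalance is large beside the effect sought.

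The COVID-19 items cannot stand in for period. Dyads who finished before version 1.8 could not have answered them, although dyads straddling the switch could have, since 7.2 asks them at visits 3 and 4 as well.

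**Working it through.** **1. The plan's own figure.** Inputs from 10.5: 20 teams, 15 dyads each, ICC .05, alpha .05 (taken as two-sided), power .80, δ = .45.
- SE = √[4 × (0.05 + 0.95/15)/20] = 0.1506 SD.
- With a noncentral t on 18 df, the detectable effect is 0.446 and power at .45 is 80.7%. The stated .45 reproduces.

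**2. Assumptions.** The documents do not date year 1, give no counts before and after June 2020 and state no period effect. That there was enrolment on both sides is implied by the transition wording in 13.3.2 and by the run of recruitment revisions. The values below are illustrative.

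**3. Utilisation.** Let d be the fall in the rate after the switch, and s the share of an arm enrolled after it. Then observed ratio = true ratio × (1 − d·s_int)/(1 − d·s_ctl), with true ratio 0.90.

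| s_int / s_ctl | d = 0.2 | d = 0.4 |
|---|---|---|
| .45 / .55 | 0.91/0.89 = 1.022, observed 0.92 | 0.82/0.78 = 1.051, observed 0.95 |
| .40 / .60 | 0.92/0.88 = 1.045, observed 0.94 | 0.84/0.76 = 1.105, observed 0.99 (0.995) |

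With d = 0 there is no distortion. With the shares reversed, the 10-point gap gives 0.90/1.022 = 0.88 to 0.90/1.051 = 0.86, which exaggerates the benefit.

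**4. How likely such gaps are.** A simulation had 10 teams per arm, each closing at 15. Assumed: between-team accrual CV 0.3 to 0.6, mean time to 15 cases about 29 of 39 months, switch at one third to two thirds of the window, no stratification.
- Equal accrual in both arms: mean gap 0. The gap exceeds 10 points in 20 to 38% of trials and 20 points in 1 to 9%.
- One arm filling 1.5 times faster: mean gap 8 to 18 points, above 20 points in 8 to 43% of trials.

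**5. Quality of life, unadjusted day-60 comparison.** Bias = gap × period effect in SD. The QOL-AD SD is 5.9 (10.5). The error rates treat the gap as fixed by arm.
- 0.10 × 0.3 = 0.03 SD = 0.18 points, 7% of .45. Type I error 5.4%; power 75% if it masks a true .45.
- 0.20 × 0.3 = 0.06 SD = 0.35 points, 13% of .45. Type I error 6.6%; power 69%.

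**6. Quality of life, change from baseline.** A dyad seen virtually at both day 0 and day 60 carries a constant mode effect at both visits, so it cancels. It remains for dyads straddling the switch. At the planned 9 dyads a month and about 2 months of follow-up that is some 18 of 345 (5%), assuming even accrual.

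**7. Stratification.** Utah has 5 teams and Miami 3 (Protocol Summary). Neither can split equally, so differences between agencies in enrolment timing can enter the arm contrast.

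**The case against.** The plan's wording on baseline covariates is open, so period could be entered without any amendment. That is true, but nothing pre-specifies it. With no SAP, the choice would be made after the data are seen.

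For quality of life, 4.2.1 frames the endpoint as a baseline-to-60-day difference, and 10.4.1 chooses mixed models to handle factors that are constant over time. A constant mode effect then largely drops out. This stands. It does not cover utilisation, which is compared at 30 and 60 days rather than as a change. Nor does it cover the day-60 comparison on which 10.4.1 focuses, dyads that straddle the switch, or a period effect on the change itself.

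A reader might infer that trained teams recognise more dementia, fill sooner and so bias the result. The documents do not show this:
- Since version 1.6 clinicians are not the point of referral. A central agency contact is, and the research team settles eligibility with a caregiver-rated QDRS (5.4, 7.2.1).
- Supply is ample by the figures in 10.5: 20,000 × 0.30 × 39/12 = 19,500 patients, of whom 345 is 1.8%.

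Some route remains. The start-of-care nurse's report feeds the referral list, and only intervention teams are trained and equipped to assess dementia (6.1.2, 6.1.3). Arm-dependent accrual is a possibility, no more.

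Fast-filling teams are not in the plan either. Section 5.4 implies, per team per month, 5/12 to 6/12 = 0.42 to 0.50 at VNAHG, 2/5 to 3/5 = 0.40 to 0.60 in Utah and 1/3 to 2/3 = 0.33 to 0.67 in Miami. The overall average, 345/(39 × 20) = 0.44, would keep a team recruiting its 17 or so dyads for the whole window. But these are forecasts, and no rule paces the teams to them.

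Stratification by agency and location limits timing differences, though incompletely.

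**Conclusion.** The point holds as a missing pre-specified term, with modest exposure. Mode and eligibility changed during enrolment, allocation does not balance calendar time, and no planned model carries it. Imbalance would arise mainly by chance, and systematically only if accrual depends on arm.

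Under the assumed 20 to 40% fall in utilisation, a 10-point gap moves a true rate ratio of 0.90 to 0.92 to 0.95, or to 0.88 to 0.86 in the other direction. Gaps above 10 points are quite possible under equal accrual.

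Three stronger readings should not be drawn:
- That a real 10% reduction would be erased. The 0.94 to 1.00 range needs a 20-point gap, an unlikely extreme if accrual is equal.
- That the quality-of-life result shifts by 0.06 SD. That figure needs the same gap and applies to the day-60 comparison; a constant mode effect does not carry it into the change from baseline.
- That every measurement changed mode. QDRS screening was already by telephone from version 1.3, and home-visit counts and patient comorbidities come from the chart.

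**What to change.** In 10.4.1, name enrolment period as a fixed effect in the adjusted models for all primary and secondary outcomes. Give it three levels by the dyad's visits relative to its site's switch to virtual visits: before, straddling or after. Report its distribution by arm and by team, and give the arm effect by period as a sensitivity analysis.

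The cost is one or two degrees of freedom and a sentence or two of text. The enrolment date is already recorded, so there are no new data, and N stays at 300 completers.

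Two limits should be stated with it. A period term does not make the 3D-CAM and FAM-CAM interchangeable for delirium, and it would not undo selection if training did change who is identified. The stopping rules in 5.6 and 10.5 should also be reconciled, since either leaves the teams' calendar spans free to differ.

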### **4.2 Study Endpoints**

#### **4.2.1 Primary Study Endpoints**

Given that this is a dyadic, implementation science intervention, it is not appropriate to look at a single primary endpoint. There are therefore 3 primary endpoints that will be examined in this study. For the Aim 1 primary endpoint, PWD QOL, a 0.5 SD difference between the baseline and 60 day visit would be clinically meaningful based on prior studies and therefore considered a positive outcome. For the Aim 2 primary

CONFIDENTIAL

This material is the property of the NYU School of Medicine and Langone Medical Center. Do not disclose or use except as authorized in writing by the study sponsor  
 Interventional Template Version: 28 APR 2017

endpoint, informal caregiver QOL, given its rate of variability and floor and ceiling effects, a 0.5 SD difference between the baseline and 60 day visit would be clinically meaningful and therefore considered a positive outcome. For the Aim 3 primary endpoint, a 10% reduction in readmissions and ER visits at 60 days will be considered a clinically meaningful positive outcome. This would result in 220 fewer ER visits and 63.8 fewer admissions per 1000 patients based on prior evidence.

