### 10.4.2 Safety Analyses

We will perform interim analyses using descriptive statistics and two-sided t-tests, monitoring for a significance of 0.05 starting at the end of year 1 of the grant for safety purposes. These results will be presented unblinded to the DSMB.

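### Section 10.4.1 allows a correlated outcome measured after allocation to be added to the mixed model, without saying how it enters or that the resulting arm coefficient is not the program effect

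*Combined protocol and SAP*

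**What the plan says.** Section 10.4.1 sets out, in this order: unadjusted comparisons between arms; a mixed-model time trend for primary and secondary outcomes; and the same analyses adjusted for baseline variables. It then adds correlation analyses, whose stated purpose is exploration, for two pairs: pain with BPSD, and PWD QOL with caregiver QOL. Scores are to be plotted over time and then, "if a significant correlation is present through adding to our mixed effect model". The section does not say whether the partner score becomes a covariate or a second response, at which time point it enters, or what will be done with the arm coefficient from that model.

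The only linear mixed model introduced by then is the time-trend model. The Protocol Summary names the same kind of model as the analysis for all non-utilization outcomes.

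All four variables are outcomes of the trial. Section 4.2.1 states: "There are therefore 3 primary endpoints that will be examined in this study". PWD QOL is the primary outcome of Aim 1 and caregiver QOL that of Aim 2. Pain and individual BPSDs are secondary for Aim 1 (Section 3.2). Table 2 schedules both QOL scales at days 0 and 60 only, so a QOL score followed over time includes the day-60 endpoint.

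Section 10.4.9 lists the interplay of caregiver and PWD outcomes as exploratory. Section 10.1 says that no formal SAP will be completed.

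**The concern.** A covariate affected by treatment changes what the arm coefficient means. With caregiver QOL in the PWD QOL model, the coefficient compares arms among dyads with the same caregiver QOL, so the part of the effect shared by the two outcomes is taken out. If the program improves both, each conditional effect shrinks. If it improves only caregiver QOL, the conditional effect on PWD QOL turns negative although the true effect is zero. Neither number answers Aim 1 or Aim 2.

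The step also depends on a significance test in the trial data, so whether this model exists is not fixed in advance. A report could then hold three estimates for each QOL outcome (unadjusted, baseline-adjusted, partner-adjusted) with no stated rule on which one is the program effect.

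**Working it through.** **Inputs from the documents.** Section 10.5 plans "with a power of .80, an alpha of .05". It says the design "would require 15 dyads per cluster, and 20 clusters (10 per arm) at 60 days", which is 300 completing dyads, to detect 0.45 SD. The authors "calculated all power with an intra-class coefficient of .05". The QOL-AD SD is 5.9. Sidedness is not stated for the main analysis. Two-sided testing is assumed here; Section 10.4.2 mentions it only for the interim safety tests ("two-sided t-tests, monitoring for a significance of 0.05").

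**Assumptions.** The documents give no correlation between PWD and caregiver QOL, so rho (within arm) is varied. The two outcomes have equal SDs, scores are taken at day 60, and the effect on caregiver QOL is set to 0.45 SD or 0.

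**Step 1: reproduce the plan's power.** In SD units,

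SE = sqrt(4 × [ICC + (1 − ICC)/n] / J) = sqrt(4 × [0.05 + 0.95/15] / 20) = 0.1506.

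The noncentrality is 0.45/0.1506 = 2.99. With a noncentral t on 20 − 2 = 18 df, power is 0.807 against the stated 0.80. The smallest effect detectable with 80% power is 0.446 SD against the stated 0.45. The plan's figure is confirmed.

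**Step 2: effect after conditioning.** Let d1 and d2 be the true effects on PWD and caregiver QOL. Regressing the first score on arm and the second score gives

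conditional effect = d1 − rho × d2, with SE = 0.1506 × sqrt(1 − rho²).

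This treats the slope on the partner score as known.

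| d1 | d2 | rho | conditional effect (SD) | QOL-AD points | rejection rate |
|---|---|---|---|---|---|
| 0.45 | not added | – | 0.45 | 2.66 | 0.81 |
| 0.45 | 0.45 | 0.3 | 0.45 − 0.3 × 0.45 = 0.315 | 1.86 | 0.55 |
| 0.45 | 0.45 | 0.5 | 0.45 − 0.5 × 0.45 = 0.225 | 1.33 | 0.37 |
| 0 | 0.45 | 0.3 | −0.135 | −0.80 | 0.145 |
| 0 | 0.45 | 0.5 | −0.225 | −1.33 | 0.37 |
| 0.45 | 0 | 0.5 | 0.45 | 2.66 | 0.90 |

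The last row matters: if the program does not move the added outcome there is no bias, and some precision is gained.

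**Step 3: simulation check.** Mixed models were fitted to 20 clusters of 15 with ICC 0.05, 200 runs per case. For d1 = d2 = 0.45 and rho 0.5, the mean effect fell from 0.454 to 0.222 and the rejection rate from 0.87 to 0.39. For d1 = 0, d2 = 0.45 and rho 0.5, the mean was −0.231, with significant apparent harm in 42% of runs. For d1 = 0.45, d2 = 0 and rho 0.5, the mean was 0.457. The means match Step 2.

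**Step 4: the trigger.** With 300 dyads, a correlation is significant at 0.05 when |r| exceeds 0.113. Allowing for a design effect of 1 + 14 × 0.05 = 1.7, the effective number is 300/1.7 = 176 and the threshold is 0.148. Modest correlations between the two QOL scores would therefore trigger the step. The 300 does not carry over to pain and BPSD, because pain is measured by the BPI or the PAINAD according to the QDRS score and each instrument covers only part of the sample.

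**The case against.** The strongest reply is that this is not the effect analysis. The sentence gives its purpose as exploring a relationship, comes after the analyses that measure the program's effect, and does not replace them. The adjustment meant to sharpen the effect estimate is limited to baseline variables. Section 10.4.9 already treats cross-outcome work as exploratory, and Section 10.3 sets up a combined data set for dyad interactions. The sentence also does not say covariate: the plan speaks of multivariate mixed models, and a joint two-response model fits that word and leaves each arm effect unbiased.

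Most of this stands. A reader might infer that the plan will report a shrunken or falsely harmful effect as its primary result. The documents do not support that: no sentence makes this coefficient the program effect, and the unadjusted and baseline-adjusted estimates are not biased by a later model. Nor do they show that the trigger will almost always be met, since that depends on a correlation they do not give.

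The gap that remains is one of silence. The covariate reading is at least as natural: Section 2.2.1.1 uses multivariate for single-outcome regressions with control variables, and a joint model would need no significance test before it is fitted. The step sits in the general approach rather than in Section 10.4.9, no model is named as primary, and no SAP will follow to settle it.

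**Conclusion.** The point holds as a needed clarification, short of a must-fix error. As written, Section 10.4.1 lets a post-allocation outcome that the program is meant to change enter the mixed model, and nothing says the resulting arm coefficient is not an effect estimate.

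If the partner score enters as a covariate and that coefficient is read as the program effect, a true PWD QOL effect of 0.45 SD would appear as 0.315 SD (rho 0.3) or 0.225 SD (rho 0.5) when caregiver QOL also improves by 0.45 SD. A true null would appear as −0.135 or −0.225 SD. These sizes rest on assumed correlations, equal SDs and a day-60 comparison. With baseline scores in the model, rho would be the correlation conditional on baseline. The bias vanishes if the program leaves the added outcome unchanged, or if both outcomes are modelled jointly as responses.

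**What to change.** In Section 10.4.1, end the correlation sentence before the clause on the mixed model, and add: arm effects on all outcomes are estimated only from models whose covariates were measured at baseline. Saying in the same place whether the unadjusted or the baseline-adjusted mixed model is primary would close the rest of the gap.

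Move the pain–BPSD and dyad QOL analyses to Section 10.4.9. Specify there either a joint two-outcome mixed model or an association model labelled exploratory, fitted whether or not a correlation test is significant. Add that any arm coefficient conditional on a post-allocation outcome will not be reported as the program effect.

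The cost is about two sentences plus the move. It needs no new data, no added sample size and no change to study conduct.
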